9.3.4 Safety Analysis

The analysis of safety data (AE, TEAE, SAE, clinical laboratory parameters, ECG parameters, vital signs, and physical exam) will be descriptive and performed on the safety population. The adverse events incidence, overall and per CTCAE grade, will be presented. The attribution to the test drugs, time-of-onset, duration of the event, its resolution, and any concomitant medications administered will be reported.

Events will be reported on per-individual basis, i.e. counting individuals rather than events. This means that even if a patient suffers the same event repeatedly during the follow-up, the event will be counted only once. Repeated events in patients will be summarized according to the following rule: if a patient suffers the same event more than once, the event will be assigned the worst severity, the closest relationship to the drug and the earliest starting date. In the listings, however, all occurrences of the events will be shown.

All AEs reported will be classified using frequency and intensity, with the most recent version of the MedDRA and listed together with information on onset, duration, seriousness, expectedness, relationship, outcome, and countermeasures taken. Serious adverse events will be listed separately.

The absolute and relative frequencies of participants with any AEs will also be listed. Furthermore, the absolute and relative frequencies for participants with AEs will be provided by System Organ Class and Preferred Term according to the MedDRA. Similarly, degrees of intensity, causal relationship with the test drugs, and the countermeasures taken for each AEs will be tabulated for each treatment. The time of onset of AEs after treatment and their duration will be evaluated on a categorical basis.

All clinical laboratory parameters will be analyzed descriptively. Summary statistics for baseline, on-treatment, and change from baseline in laboratory, vital signs, and ECG parameters will be provided by treatment group in table format. Mean change from baseline over time will be plotted with the corresponding standard errors. Values of safety laboratory parameters and urinalysis outside the reference range will be flagged as H (above the reference range) or L (below the reference range) in the listings. A summary will be prepared by counting both the values out of reference range and the number of patients in whom one or more abnormalities occurred after treatment. Shift tables may be provided for the changes with respect to reference range for the following groups of parameters: hematology, clinical chemistry, and urinalysis. For all parameters, these shifts may be tabulated within each treatment and by visit, for the comparison before and after treatment.

Patients with abnormalities for vital signs, ECG, physical exams or clinical laboratory parameters will be tabulated and listed in different tables. Abnormality ranges will be defined for actual values and for changes from reference.

9.3.5 Pharmacodynamics Analysis

All analyses of pharmacodynamics will be based on the Pharmacodynamics Analysis Population (PDS).

Statistical descriptions of PLT and their differences from baseline at each time point will be performed, providing the number of cases, mean, standard deviation, coefficient of variation, median, quartiles, minimum, and maximum values. Calculate the maximum value of the change in platelet count relative to baseline (E_{\max}), the time to peak (ET_{\max}), and plot a line graph of the mean with standard deviation.

Line graphs of changes in PLT at each visit for each participant.

9.3.6 Immunogenicity Analysis

ADAS will be used to summarize the immunogenicity data of the participants at different time

points. According to the planned timepoints, the number and percentage of ADA positive will be summarized and listed. If possible, the titers and NAb for ADA-positive will be further analyzed and summarized.

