Participants will undergo screening, admission (baseline), administration and follow-up observation period. Participants will sign an informed consent form before any study procedures are performed. During screening, all participants will be screened for study eligibility within 28 days prior to administration. Eligible participants will be admitted to the clinical study ward no later than one day prior to dosing (D-1). Participants need to fast for at least 10 hours prior to dosing and 4 hours after dosing. Single abdominal subcutaneous injection of the study drug will be given on D1. The administration and follow-up observation period will be 29 days (D1~D29). Participants may be discharged at D7 at the judgment of the investigator. PK blood samples will be collected from D-1 to D14, tolerance and safety will be observed from D1 to D29, and blood samples for PD and anti-drug antibody (ADA) will be collected from screening to D29. After completion of relevant assessments on D29, participants will be considered as having completed this study.

Design of PK study

PK study is required for all participants in this study. PK blood samples will be collected at the following specified time points: D-1, before administration (D1), 2 h, 5 h, 8 h, 10 h, 12 h, 16 h, 24 h, 36 h, 48 h, 72 h, 96 h, 120 h, 144 h, 168 h, 216 h, 264 h and 312 h after administration.

Design of PD study

PD blood samples will be collected from participants in this study at specified time points: D-28 ~ D-2, D-1, D4, D8, D10, D14, D22 and D29; PD blood samples will be collected in the early morning for hematology, in which platelet count will be taken as PD indicator.

Design of immunogenicity study

Immunogenicity blood samples will be collected from participants in this study at specified time points: D-1, D14, and D29. Samples may be further characterized to determine the titer and the presence of neutralizing antibodies (NAb) if positive for ADA.

Data Monitoring / Other Committee: No

Statistical methods:

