Platelet count (PLT) at each time point and its change from baseline will be statistically described, and the number of observations, mean, standard deviation, coefficient of variation, median, quartiles (Q1 and Q3), minimum and maximum will be provided. Maximum platelet count change from baseline (E_{max}) and time to peak platelet count (ET_{max}) will be calculated, and descriptive statistics will be performed. In addition, ET_{max} will be only presented as median, minimum and maximum values. A line graph with mean and SD will be generated. Line plots of the changes in platelet count by visit for each participant will also be displayed.

Immunogenicity Analysis

ADAS will be used to summarize the immunogenicity data of the participants at different time points. According to the planned timepoints, the number and percentage of ADA positive will be summarized and listed. If possible, the titers and NAb for ADA-positive will be further analyzed and summarized.

Safety and tolerability analysis

The analysis of safety data (adverse event [AE], treatment emergent adverse event [TEAE], serious adverse event [SAE], clinical laboratory parameters, electrocardiogram [ECG] parameters, vital signs, and physical examinations) will be descriptive and performed on the safety population. The adverse events incidence, overall and per Common Terminology Criteria for Adverse Events (CTCAE) grade, will be presented. The attribution to the test drugs, time-of-onset, duration of the event, its resolution, and any concomitant medications administered will be reported.

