3 OBJECTIVES AND ENDPOINTS

Table 5 Objectives and Endpoints

Objectives	Endpoints
Primary	
To evaluate the PK profile following a single dose of rhTPO in healthy Caucasian	PK concentration-time profile and PK parameters: T_{max} , C_{max} , $t_{1/2}$, MRT, AUC_{0-t} , $AUC_{0-\infty}$, V_d/F , K_e , CL/F , $AUC_{\%Extrap}$.
Secondary	
To evaluate the PD profile following a single dose of rhTPO in healthy Caucasian	PLT counts and changes in PLT over time.
To evaluate the safety and tolerability following a single dose of rhTPO in healthy Caucasian	Incidence and severity of AEs and SAEs, physical examination, vital sign, clinical laboratory test, ECG, ISR
To evaluate the immunogenicity profile following a single dose of rhTPO in healthy Caucasian	Incidence of the development of ADAs and NAb (if applicable) to rhTPO

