9.1 Sample Size Determination

This is an exploratory Phase I clinical study of the pharmacokinetics, pharmacodynamics, safety and tolerability of a single dose of Recombinant Human Thrombopoietin for Injection (rhTPO) in a single-center, single-arm, open-label, single-dose design in healthy volunteers from a Caucasian population. The sample size of this study is not based on statistical hypothesis and the study is planned to enrol approximately 22 healthy Caucasian participants.

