9.2 Populations for Analyses

For purposes of analysis, the following populations are defined:

Table 8 Populations for Analysis

Analysis Set	Description
Safety analysis set (SS)	All participants enrolled and receiving the full dose of study drug and have at least one post-dose safety assessment. SS will be used for demographics, baseline characteristics, and safety analyses.
PK concentration set (PKCS)	All participants enrolled and receiving the full dose of study drug with at least one evaluable concentration data during the study. PKCS will be used for PK concentration analysis.
PK parameter sets (PKPS)	All participants enrolled and receiving the full dose of study drug with at least one evaluable PK parameter during the study. Participants whose PK parameter results affected by major protocol violations will be excluded from the PK parameter set. PKPS will be used for PK parameter analysis.
PD analysis set (PDS)	All participants enrolled and receiving the full dose of study drug with at least one evaluable PD data during the study, but participants whose PD e results affected by major protocol violations will be excluded. The PDS will be used for the pharmacodynamic analysis.
Immunogenicity Analysis Set (ADAS)	Participants with at least one immunogenicity result in the safety analysis set. ADAS will be used for immunogenicity analysis.

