9.3 Statistical Analyses

This section is a summary of the planned statistical analyses of the most important endpoints including primary and secondary endpoints.

There is no statistical hypothesis associated with the study objectives. As such, no statistical tests will be performed. The analyses of safety, efficacy, biomarker and pre-defined subgroups will primarily be descriptive.

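### The immunogenicity endpoint is the incidence of ADA development, but the only analysis stated is the percentage ADA-positive at each visit, which does not determine that incidence

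*Protocol*

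**What the plan says.** Protocol section 3 (Table 5) and the synopsis give the endpoint for the secondary immunogenicity objective as "Incidence of the development of ADAs and NAb (if applicable) to rhTPO".

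The analysis appears in section 9.3.6 and, in the same terms, in the synopsis. The general statement is "ADAS will be used to summarize the immunogenicity data of the participants at different time points". The specific one is that, by planned timepoint, "the number and percentage of ADA positive will be summarized and listed". Titres and NAb in ADA-positive participants are to be analysed further if possible.

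The sampling schedule is in the synopsis ("Immunogenicity blood samples will be collected from participants in this study at specified time points: D-1, D14, and D29") and in Table 3. One of the three timepoints is therefore before dosing. Table 1 places the last sample at D29 or early withdrawal.

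The analysis set in section 9.2 (Table 8) is "Participants with at least one immunogenicity result in the safety analysis set". It requires neither a D-1 result nor a post-dose result.

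The study is descriptive. On inference, section 9.3 says "As such, no statistical tests will be performed". On size, section 9.1 says "The sample size of this study is not based on statistical hypothesis and the study is planned to enrol approximately 22 healthy Caucasian participants".

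**The concern.** Development of antibodies is a per-participant quantity: a person without ADA before dosing has it afterwards. The percentage positive at a visit is a prevalence. It includes anyone who was positive before dosing and still is, and it does not combine people who turn positive at different visits. The protocol thus names one quantity as the endpoint and describes the calculation of another. It does not define treatment-emergent ADA, separate baseline positives at D14 and D29, or count participants positive at any post-dose visit.

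The rest of section 9.3 does use a baseline or a per-participant count where one is needed. Adverse events are counted per individual, laboratory abnormalities are also counted by participant after treatment, platelets are analysed as change from baseline, and PK concentrations are corrected for endogenous TPO. Pre-existing positivity is not designed out either, since no eligibility criterion requires a negative ADA result.

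What is at stake is whether the secondary immunogenicity objective is answered by the endpoint named for it. Sample size and error rates are unaffected.

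**Working it through.** The plan states no ADA figure, so there is none to reproduce. The check is whether the by-visit percentages determine the incidence.

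**Inputs from the protocol.** N = 22 (section 9.1); ADA samples at D-1, D14 and D29 (synopsis, Table 3); output is number and percentage positive per timepoint (section 9.3.6).

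**Assumed inputs.** The protocol gives no rate of pre-existing or new ADA, so every count below is an assumption. Samples are taken as complete. Let
- b = positive at D-1 and at both later visits,
- a = new at D14 only,
- c = new at D29 only,
- d = new and positive at both D14 and D29.

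**Formulas.**
- Positive at D-1: b/N
- Positive at D14: (b + a + d)/N
- Positive at D29: (b + c + d)/N
- Incidence of development: (a + c + d)/N, or (a + c + d)/(N − b) among baseline-negatives

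With n14 and n29 the counts positive at the two post-dose visits, the number of new positives is n14 + n29 − 2b − d. The table supplies n14, n29 and b. It does not supply d, the overlap between the two visits.

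**Results with N = 22.**

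| Assumed pattern (b, a, c, d) | D-1 | D14 | D29 | Incidence |
|---|---|---|---|---|
| Two lasting pre-existing, none new (2, 0, 0, 0) | 2/22 = 9.1% | 2/22 = 9.1% | 2/22 = 9.1% | 0/22 = 0% (0/20 of baseline-negatives) |
| One new at D14 only, one at D29 only (0, 1, 1, 0) | 0% | 1/22 = 4.5% | 1/22 = 4.5% | 2/22 = 9.1% |
| The same two new at both visits (0, 0, 0, 2) | 0% | 2/22 = 9.1% | 2/22 = 9.1% | 2/22 = 9.1% |
| Two lasting pre-existing, one new at D14 only, one at D29 only (2, 1, 1, 0) | 2/22 = 9.1% | 3/22 = 13.6% | 3/22 = 13.6% | 2/22 = 9.1% (2/20 = 10.0% of baseline-negatives) |

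In the first row each post-dose percentage is above the incidence; in the second each is below it. In the third they agree, because nobody is positive at D-1 and the same people are positive at both later visits. The third row also shows that the table is ambiguous. Its figures of 0%, 9.1% and 9.1% would look the same if two participants were new at D14 only and two others at D29 only, and the incidence would then be (2 + 2)/22 = 18.2%.

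**The case against.** The strongest reply is that section 9.3 calls itself a summary and a statistical analysis plan is to follow. Rules for induced or boosted antibodies, the titre threshold and the handling of missing baselines are ordinary content for that plan. This stands for those details, and it means the gap is shown for the protocol only. It does not remove the mismatch. Section 9.3 says that it covers the secondary endpoints, section 9 has the analysis plan written from the protocol, and an analysis plan that followed 9.3.6 to the letter would not report the endpoint in Table 5.

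Three stronger readings are tempting, and the documents do not support them.

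- A reader might infer that pre-existing positives would be presented as caused by the drug. D-1 is a planned timepoint, so its percentage stands beside those for D14 and D29, and nothing in the protocol attributes later positivity to the drug.
- A reader might infer that the incidence would be lost. Results are also to be listed, and with about 22 participants and three samples each, conversions can be counted from the listing.
- A reader might infer from the loose analysis set that someone with only a D-1 result would dilute the post-dose percentages. The statistical methods in the synopsis keep missing values out of percentages unless otherwise specified, so that person does not enter the D14 or D29 figure.

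It is also fair to say that the counts above are invented, and that with no baseline positives and full overlap of visits the two quantities coincide.

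**Conclusion.** The point holds as a mismatch between two things the protocol states: the endpoint is an incidence of development, and the analysis given is a prevalence by visit. The second does not determine the first, and a visit figure can lie above or below the incidence. With 22 participants each person is worth 1/22 = 4.5 percentage points, and the two main illustrations differ from the incidence by 9.1 and 4.5 points. Those sizes rest wholly on assumed ADA counts and complete sampling.

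The consequence is minor to moderate. The endpoint is secondary and descriptive, and the D-1 percentage and the listings allow the incidence to be rebuilt. A named endpoint should still be computed by its stated analysis, not reconstructed by the reader once the data are known, so the change is worth making.

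**What to change.** In section 9.3.6 and the immunogenicity paragraph of the synopsis, add the number and percentage of participants who are ADA-negative at D-1 and ADA-positive at any post-dose visit (D14, or D29/early withdrawal). The denominator is participants with a D-1 result and at least one post-dose result.

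Report participants positive at D-1 separately. If titres are determined, give a boosted category among them based on a rise in titre, with the threshold left to the statistical analysis plan. Report NAb the same way where it is tested. Keep the by-visit table as a supporting display.

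The cost is one or two sentences and one table row, with no new visit or blood draw. Only the boosted category depends on something not yet assured: titre assays are optional in Table 3, section 8.2 and section 9.3.6.

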9.4 Data Monitor Committee

No.

10 SUPPORTING DOCUMENTATION AND OPERATIONAL CONSIDERATIONS

A 1 Regulatory and Ethical Considerations

- This study will be conducted in accordance with the protocol and with the following:
 - Consensus ethical principles derived from international guidelines including the Declaration of Helsinki and Council for International Organizations of Medical Sciences (CIOMS) International Ethical Guidelines
 - Applicable Council for Harmonisation (ICH) Good Clinical Practice (GCP)
 - Applicable laws and regulations
- Prior to the commencement of the clinical study, the study protocol, informed consent form and other information provided to the participants are subject to review and approval by the Ethics Committee, and the relevant approvals are provided to the sponsor. Any modifications to the protocol and ICF during the study also need to be reported to the IEC for approval before implementation.

A 2 Informed Consent Process

The investigator or his/her authorized representative must obtain an informed consent form signed by the participants participating in the study and explain to the participants the nature, purpose, potential hazards, and benefits of the study, and must let the participants know that they may withdraw from the study at any time without restriction. If the participant is unable to sign the informed consent form, the participant's legal representative must sign the informed consent form. If the participant or their legal representative is unable to read the informed consent form, an impartial witness must be present throughout the informed consent process. After the participant and his/her legal representative verbally agree to participate in the study, the impartial witness must sign the informed consent form and ensure that the participant and his/her legal representative are fully informed and understand the contents, and that the participant is aware that they may withdraw from the study at any time without restriction. If safety results result in a significant change in the risk/benefit assessment, the informed consent form is reviewed and changed as necessary, and all participants (including those already receiving treatment) must be informed of the updated information and sign the new informed consent form before continuing with the study.

Both “telehealth discussion and signing” and “in-person discussion and signing” are available.

Two copies of the informed consent form should be signed and one should be kept with the participant, and the other copy of the informed consent form should be kept with the study records at the site. The informed consent process should be documented in the participant's medical or other original records.

A 3 Management of Investigational Drug

A 3.1 Packaging and Labeling

All investigational drugs will be provided to the investigator by Shenyang Sunshine Pharmaceutical Co. or its designee. The following information should be stated on the drug label:

- Study/Protocol Number
- Specifications
- Storage instructions
- Expiry/Retest Date
- Lot number
- Description of "Clinical study material - Study Use Only", or similar statement
- Name and address of study sponsor/investigational drug manufacturer

The Investigator or his/her designee shall not provide investigational drugs to any participant not enrolled in the study, or to any physician or scientist not appointed to this study.

A 3.2 Storage

The investigational drug shall be kept in a secure locked cabinet or sealed container with strictly limited access only to the investigator or his/her designated personnel. Neither the investigator nor his/her authorized personnel shall provide the drug to any participant not enrolled in this study protocol.

Investigational drugs should be stored under the conditions specified on the investigational drug label.

A 3.3 Traceability

The investigator, or designee, must maintain a detailed inventory record of receipt, distribution, use, and retrieval in order to provide assurance to the sponsor that the investigational drug has not been distributed to any person other than a participant who meets the deadlines and conditions set forth in this study protocol.

The investigator must securely store the drugs supplied for the conduct of the study. For

investigational drugs sent to the study site, the investigator or designee shall confirm the quantity sent, the date of acceptance, and that the drug supply will be undamaged and uncontaminated in transit, and shall sign and date the appropriate documentation.

All used and unused/unopened medication containers must be carefully inventoried and kept at the site until collected by the sponsor or disposed of.

A 3.4 Restitution

Once the study is nearing completion or termination, all unused and/or partially used study medication can be returned to the sponsor or disposed of.

A 4 Data Management

A 4.1 Data Collection

The Web-based Electronic Data Capture (EDC) Systems will be used to collect, store, and manage clinical data. The EDC database builder will establish the electronic case report form (eCRF) in EDC according to the protocol. Before EDC database goes live, the eCRF will be approved by Project Managers, Medical Reviewer and Biostatistician etc. The DM will conduct the EDC training and introduce the eCRF completion guideline for project managers, clinical research associates (CRA), investigators etc. After receiving the training, the relevant personnel can log into the EDC system and then enter the data into the eCRF. The EDC system can automatically verify the data in the eCRF and generate corresponding prompt messages. After the investigators modify and verify the entered data, the Principal Investigator or his/her authorized Investigators will sign electronically to confirm the data.

A 4.2 Data Review

The CRAs review the data entered into the eCRF by investigators for completeness and authenticity, and if necessary, query message to ask investigators to verify and revise until the data are accurate, complete and clean;

The data manager reviews the data entered into the eCRF by investigators for consistency and accuracy, and if necessary, query message to ask investigators to verify the changes until the data is accurate, complete and clean;

Medical reviewers to review eCRF data from medical expertise, if necessary, a query to ask investigators to verify modifications, until the data are accurate, complete, and clean;

All data issues should be confirmed before the database lock. The audit trails are required for all data changes and related operations.

A 4.3 Database Locking

If there is a data review meeting or other form of data review communication, the principal investigator, medical manager, project manager, data manager, and statistician should confirm any protocol deviation events that occurred in the trial and the impact on the statistical analysis dataset, and confirm that the database is complete and accurate before co-signing the relevant documents to lock the database. In principle, no further changes to the locked database are allowed. Problems found after data locking can be updated in the database or explained in the report after confirmation, and a written record will be kept. In order to ensure the security of the data, unrelated persons are not allowed to approach and modify the data, and the data must be backed up.

A 5 Quality Control

A 5.1 Monitoring

The sponsor's monitor or representative/designee will visit the site prior to enrolment of the first participant at the site and will conduct on-site visits at a planned frequency during the course of the study, as well as periodic telephone and written communications.

After the investigator or clinical research coordinator (CRC) completes data entry, the supervisor conducts online for raw data approval (SDV), and the supervisor, medical staff, and data manager conduct data verification and send data queries online. After the query is sent, the investigator verifies the raw data and resolves the query online.

A 5.1.1 Data Requirements for Supervisor Surveillance

- 1) Supervisors check for informed consent and screening of participants for inclusion during the study;
- 2) Verify that all eCRFs are completed correctly and agree with the original information;
- 3) All errors or omissions have been corrected or noted, signed and dated by the investigator;
- 4) Dose changes, therapeutic alterations, concomitant, and intercurrent illnesses should be identified and documented for each participant;
- 5) Verify that both withdrawals and lost visits of enrolled participants should be accounted for in the eCRF;
- 6) Confirmation that all adverse events have been recorded and that serious adverse events have been reported and recorded;
- 7) Verify that investigational drugs are supplied, stored, dispensed, and withdrawn in

accordance with the relevant regulations, and record accordingly;

8) The eCRF form is completed by the investigator or his/her authorized personnel and the eCRF must be completed for each enrolled case.

A 5.2 Auditing

Both sponsors and investigators should establish their own quality assurance systems, fulfil their respective responsibilities, and strictly follow the clinical study protocols and adopt the appropriate standard operating procedures to ensure the implementation of quality control and quality assurance systems for clinical study.

The sponsor may conduct audits of the above clinical study process, sample testing process, data, reports and calculations in different categories as needed, taking into account the progress of the study and the results of the verification by the quality controller/supervisor. The investigator shall agree to cooperate with the audit in a reasonable manner and at a reasonable time.

A 6 Study Documentation Management

A 6.1 Study Data Acquisition and Modification

At each follow-up visit of the participant, the investigator participating in the study or his/her designee shall document in the study medical record the content of the visit to the participant, the examination and observations, etc., which shall include, at a minimum:

- 1) Documentation of the process of obtaining informed consent, including various revised consent forms.
- 2) Dates and days of follow-up visits and visits equivalent to their follow-up in the study schedule.
- 3) Overall participant status, including all significant medical findings. The severity, frequency, and duration of various adverse events and the investigator's assessment of their causal relationship with the investigational drug, study manipulation, and other concomitant medications must also be documented.
- 4) Various changes in concomitant medication or dosage levels.
- 5) A general reference to the completed operation.
- 6) Signature and date of the clinical staff member who wrote the chart entry and/or signature and date of the investigator.

In addition, clinically significant information discovered by contacting participants by telephone or other means should also be documented in the study medical record as required by the methodology described above.

Any changes to information in the study chart and other original documents should be initiated and dated on the day of the change by the investigator who authorized the change. Amendments should be made by drawing a single straight line through the incorrect data and clearly documenting the correct data. If the reason for the modification is not obvious, a brief explanation of the modification should be provided by the Investigator on the original documentation. For participants who withdraw early, only the withdrawal follow-up should be completed.

A 6.2 Original Documents

Original documentation is defined as all information contained in the original records necessary for study reconstruction and evaluation in a clinical study, as well as qualified copies of original records of clinical findings, observations, or other items. Original documentation includes progress notes, electronic data, screening records, and recorded data from automated instruments.

All original documents related to this study will be kept by the investigator. The investigator is obliged to allow study-related surveillance, audits by the sponsor or its appointees, reviews by the IEC and inspections by the competent authorities.

A 6.3 Document Management at the Study Site

Investigators are responsible for ensuring that study site documentation is maintained in accordance with GCP guidelines.

A 6.4 Record-keeping at the Study Site

The principal investigator is obliged to keep study records and data for safety information traceability and audit and visual inspection after the study has ended. The primary documentation should be kept until at least 5 years after the completion or discontinuation of the study. However, if required by relevant regulations or if requested by the sponsor, the above documents should be kept for a longer period of time. Samples, documents and computerized records should be kept in a secure area to prevent trespassing, loss or interference.

The investigator may not dispose of any records related to this study without the following permission:

- Written permission from the sponsor.
- Provide opportunities for sponsors to collect such records.

The investigator shall be responsible for maintaining adequate and accurate electronic or paper-based source documentation of all observations and data generated during this study. Such participant documentation is the basis for visual inspection by the sponsor and relevant authorities. If the investigator withdraws from the study (e.g., change of position or retirement), study-related records should be transferred to a mutually agreed upon designee. The sponsor shall be notified in writing of such transfer.

A 6.5 Record-keeping for Sponsors

The sponsor will maintain all essential sponsor-specific documents in accordance with the appropriate regulatory requirements of the regulatory authority. If the sponsor discontinues the clinical development of an investigational drug (i.e., due to any or all of the indications, routes of administration, or dosage forms), the sponsor will maintain essential sponsor-specific documentation until at least 5 years after the formal discontinuation or as required by the relevant regulations.

If the sponsor discontinues clinical development of the investigational drug, the sponsor should notify all investigators/institutions and all relevant authorities.

Important documents that are proprietary to the sponsor should be kept until at least 5 years after the completion or discontinuation of the study. However, these documents should be retained for a longer period of time if required by relevant legislation or if requested by the sponsor.

The sponsor shall notify the investigator/institution in writing of the record (original and/or study base document) retention requirements and shall notify the investigator/institution in writing when records related to the study are no longer required to be maintained.

A 7 Confidentiality

All information generated during the study shall be kept in the highest degree of confidentiality and shall not be disclosed to anyone not directly related to the study without the written permission of the participant. However, direct access may be granted to authorized management, sponsor personnel (or their representatives) and the IEC to inspect and copy these records. Only participants who have signed an informed consent form may be enrolled in this study. All applicable data confidentiality provisions must be fully complied with. All investigational drugs, participant body fluids, and/or other collected materials shall be used exclusively in accordance with the protocol of this study, unless written consent is obtained from the sponsor.

All pages of the eCRF and all reports and correspondence pertaining to participants in the study shall be distinguished only by the participant's abbreviation of name letters (The four spaces of the participant's name abbreviation should be filled in, consisting of the first two letters of the first name and the first two letters of the last name), and by the participant's number. The

investigator should keep a list of the identification codes of the participants in this study. This information shall be kept in the strictest confidence and shall be used only in case of emergency if required.

A 8 Publication Policy

Relevant data about this study will be published only with the consent of the research unit and the sponsoring organization.

